### **Objective 3: Pregnancy course and perinatal outcome**

Methodology: a longitudinal study. For pregnant women affected by COVID-19, following recovery, 4-weekly ultrasound scan for assessing fetal size, amniotic fluid volume, fetal Dopplers (umbilical artery, middle cerebral artery, ductus venosus), uterine artery Doppler and placental morphology (echogenicity, thickness, appearance) and function will be done. For first and early second trimester infected cases, a detailed fetal morphological scan will be undertaken to determine the risk of structural malformation. The following information will be collected: (i) maternal demographics including: age, weight, height, racial origin, smoking, medical history of chronic hypertension, cardiovascular disease, diabetes mellitus and respiratory disease, drug history, method of conception, parity, past obstetric history; (ii) delivery outcome: gestational age at delivery, mode of delivery, complications including stillbirth, FGR, preterm birth, preeclampsia; (iii) neonatal data: birthweight, sex, Apgar scores, cord arterial and venous pH and base excess, neonatal outcome, admission to neonatal intensive care unit (NICU), complications such as sepsis, anemia, intraventricular hemorrhage, necrotizing enterocolitis, respiratory distress syndrome, need for respiratory support, laboratory findings; (iv) COVID-19 specific data: gestational age at clinical manifestation; symptoms and signs; epidemiological history; laboratory and radiological findings; treatment measures; COVID-19 severity and outcomes; and intervals from onset of disease to hospital admission, delivery and recovery will be recorded. Results on maternal and perinatal outcomes will be summarized in counts and percentages and median and ranges. Target achievement: To date, there are 5 reported pregnant cases affected by COVID-19 in Hong Kong. We anticipate that between Hong Kong, China and Spain, we will recruit 40-50 pregnancies affected by COVID-19 with complete data according to protocol. We will learn a complete picture of the pregnancy course and perinatal outcome of cases affected by COVID-19. Such data will form the basis of counselling regarding the impact of coronavirus on pregnancy and perinatal outcome.

#### **Objective 4: Vertical transmission**

Methodology: a cross-sectional and longitudinal study. Appropriate biological samples (Table 2) will be collected using aseptic technique and tested from consented pregnant women affected by COVID-19 from above objectives (Table 3). When the biological samples that have been collected immediately after birth are negative for SARS-CoV-2, but the IgM and IgG antibodies are positive in the newborn, longitudinal follow-up of the IgG antibody concentrations in the infant is required. If the IgG antibodies in the infant become negative within 6 months, the possibility of intrauterine infection can be ruled out, and if the IgG antibodies in the infant persist till the age of 18 months or beyond, the diagnosis of congenital infection can be confirmed after exclusion of infection during infancy. Results on the rate of positive results will be summarized in counts and percentages. Target achievement: Relevant testing (RT-PCR and/or anti-SARS-CoV-2 antibodies testing) of a comprehensive collection of biological samples from the mothers and the newborns will allow evaluation of whether vertical transmission has occurred.

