Two reports suggested possible transplacental infection due to the presence of neonatal IgM antibodies and abnormal cytokine levels after birth, since IgM is not transmitted transplacentally and may have been produced by the fetus in response to in utero exposure to SARS-CoV-2. In both reports, RT-PCR of neonatal nasopharyngeal swab and maternal vaginal secretions were negative. Specifically, in the study of Dong et al., the observed decline of anti-SARS-CoV-2 IgG and IgM levels from 140.32 AU/mL (normal range is 0–10 AU/mL) and 45.83 AU/mL (normal range is 0–10 AU/mL), respectively, at 2 hours after birth to 69.94 AU/mL and 11.75 AU/mL, respectively, at 14 days of age, is not consistent with the typical profile of the body's antibody response to acute viral infection. The rapid decline of anti-SARS-CoV-2 IgG antibody level in the infant within 14 days, in addition to the decline in IgM antibody level, strongly indicates that the neonatal anti-SARS-CoV-2 IgG antibodies were derived transplacentally from the mother and their production was not actively induced by the presumed neonatal infection.

Nevertheless, there are several limitations in addressing the issue of vertical transmission as most studies reported infections in the third trimester where the interval between infection and delivery is relatively short. The risks of transplacental infection in the first and second trimesters, with a potentially longer fetal exposure time, are unclear. While most reported cases have been delivered by Cesarean section, the evidence does not suggest a clear association between neonatal SARS-CoV-2 and vaginal delivery.

With regard to whether SARS-CoV-2 infection or its disease is associated with pregnancy loss,

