### **Study coordination**

**[name]** has conceived and designed this project and will manage and coordinate all aspects of the study. For objective 1, together with **[name]**, who is the team bioinformatician, a list of eligible patients has been drawn from our DSS database. **[name]** is overseeing the recruitment of eligible patients for recruitment for objective 1. She will also collect and manage study data. For objective 3, there are currently 5 pregnant women in Hong Kong affected by COVID-19 and their pregnancy is ongoing. **[name]** will provide clinical guidance for and oversee the follow up of the affected pregnant women. **[name]** will contribute maternal and perinatal outcome data of the pregnant cases that had acquired SARS-CoV-2 infection during the first and second trimester of pregnancy from her existing cohort study in China. **[name]** from Spain has started recruitment of patients affected by COVID-19 and collection of biological samples according to the proposed protocol (objective 4). **[name]** is an academic gynecologist with an extensive research experience in pregnancy loss. She will organize for collection of POC and recruit stillbirth cases. **[name]** is a clinician scientist and **[name]** is a molecular biologist, both with a special interest in disease mechanism; together they will conduct all experiments for objective 5. **[name]** will contribute and assist with the interpretation of data for objective 5. **[name]** and **[name]** are infectious disease specialists with extensive experience in COVID-19 research. Their laboratory will be in charge of analyzing all biological samples for objectives 2,4. **[name]** is an academic pediatrician with expertise in neonatal intensive care research. He will coordinate follow up of the neonates born to mothers with COVID-19.

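### Does the Objective 4 antibody rule distort the vertical transmission rate by giving no class to infants who lose IgG between 6 and 18 months?

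*Protocol*

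**What the plan says.** The protocol's section on Objective 4 sets a follow-up rule for one group: infants whose birth samples are negative for the virus but who carry both IgM and IgG. Only IgG is then followed. At the early end, "If the IgG antibodies in the infant become negative within 6 months, the possibility of intrauterine infection can be ruled out". At the late end, "if the IgG antibodies in the infant persist till the age of 18 months or beyond, the diagnosis of congenital infection can be confirmed", on condition that infection acquired during infancy has been excluded. The planned summary is one sentence: "Results on the rate of positive results will be summarized in counts and percentages".

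The Background discusses neonatal antibodies from published reports. It gives the reasoning of two of them, that "IgM is not transmitted transplacentally and may have been produced by the fetus in response to in utero exposure". For one published newborn it then argues that the fall in IgG over 14 days, "in addition to the decline in IgM antibody level", "strongly indicates that the neonatal anti-SARS-CoV-2 IgG antibodies were derived transplacentally from the mother".

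Objective 4 states no sample size of its own. The nearest figure is in Objective 3: "we will recruit 40-50 pregnancies affected by COVID-19 with complete data according to protocol".

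**The concern.** There were two grounds for doubt.

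The first is that the rule does not cover every outcome. An infant who is still IgG-positive at 6 months and negative before 18 months is neither ruled out nor confirmed. The same seems true of an infant whose IgG persists to 18 months but in whom later infection cannot be excluded. If only confirmed infants enter the numerator and all tested infants the denominator, both are counted as non-positive. The reported risk would then be lower and look more certain than the data allow. With a few dozen infants, one or two could decide whether the study reports no transmission or possible transmission.

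The second is that ruling out infection on IgG alone is a firmer statement than the Background makes. The Background uses the fall of both antibodies and claims only a strong indication. Infants enter the rule because IgM is positive, yet IgM plays no part afterwards.

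**Working it through.** There is no planned figure for Objective 4 to reproduce, so the check has three parts.

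**1. Which outcomes does the rule cover?** The inputs are the two ages in Objective 4, 6 and 18 months. The uncovered window is 18 − 6 = 12 months.

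| IgG course | Class under Objective 4 |
|---|---|
| Negative within 6 months | Ruled out |
| Lost after 6, before 18 months | None stated |
| Still positive when follow-up ends before 18 months | None stated |
| Persists to 18 months, infection in infancy excluded | Confirmed |
| Persists to 18 months, infection in infancy not excluded | Not confirmed, because the condition fails |

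The window is real. The last row is already handled: confirmation is conditional, so the infant is not confirmed and only a name is missing.

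**2. Does the summary count the unlabelled infants as non-positive?** The summary sentence does not say whether it counts samples or infants. The surrounding text is about testing a set of biological samples from mothers and newborns, so a rate per type of sample is an equally natural reading. On that reading the infant's final class does not enter the rate. On an infant-level reading, at least three treatments are open.

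For illustration, assume no confirmed case, one infant per pregnancy, n = 40 or 50 from Objective 3, and k unlabelled infants (k is assumed; the protocol gives no value). Intervals are exact (Clopper-Pearson) 95%. For zero events the upper limit is 1 − 0.025^(1/n); for n = 40 this is 8.8%.

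| n, k | Counted negative | Counted positive | Left out |
|---|---|---|---|
| 40, 1 | 0/40 = 0% (0-8.8) | 1/40 = 2.5% (0.06-13.2) | 0/39 = 0% (0-9.0) |
| 50, 1 | 0/50 = 0% (0-7.1) | 1/50 = 2.0% (0.05-10.6) | 0/49 = 0% (0-7.3) |
| 40, 3 | 0/40 = 0% (0-8.8) | 3/40 = 7.5% (1.6-20.4) | 0/37 = 0% (0-9.5) |
| 50, 3 | 0/50 = 0% (0-7.1) | 3/50 = 6.0% (1.3-16.5) | 0/47 = 0% (0-7.5) |

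Each infant shifts the rate by 1/n: 1/50 = 2.0 points, 1/40 = 2.5 points. Objective 4 may have fewer infants than Objective 3, since the section on study coordination says the collaborator in China "will contribute maternal and perinatal outcome data of the pregnant cases that had acquired SARS-CoV-2 infection" and mentions no samples from there. At an assumed n = 20 the shift is 1/20 = 5.0 points: 0/20 = 0% (0-16.8) against 1/20 = 5.0% (0.1-24.9). These shifts show sensitivity to a choice that the protocol does not make. They are not a bias produced by a rule that it states.

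**3. Do the Background and Objective 4 conflict?** The Background case is one newborn over 14 days. IgG went from 140.32 to 69.94 AU/mL, 69.94/140.32 = 49.8% of the start. IgM went from 45.83 to 11.75 AU/mL, 11.75/45.83 = 25.6%. Both were still above the quoted normal range of 0-10 AU/mL. That is a decline. Objective 4 requires IgG to become negative, with up to 6 months to do so. The Background also treats the joint fall as untypical of a response to acute infection, so it argues in the same direction as the rule. Different observations support statements of different strength, and the two passages can stand together.

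**The case for a change.** The best case for a change is that the protocol, and not a later document, fixes both the diagnostic rule and the summary, and that the rule is incomplete for the very infants it exists to resolve. Objective 4 aims to determine the risk of vertical transmission. With so few infants, a counting choice made after the data are seen could move the result from none to some. Settling it beforehand would cost a line of wording and two table rows, and would alter no diagnostic criterion.

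Part of this stands. The 12-month window has no class, nor does an infant whose follow-up ends early, and at this sample size one infant is visible in the percentage. What does not stand is the step from no stated class to counted as uninfected: nothing in the text sets that default. Nor is the direction of error known, since a non-positive count is wrong only if the infant was truly infected. How unresolved cases are tabulated is commonly left to the statistical analysis plan, which is not available here. Table 3 and possibly part of Table 2, on which Objective 4 relies, are also not shown.

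The point about the Background is weaker. Even a three-class scheme would keep infants with early IgG loss in the excluded class, so it would change no count. The choice of diagnostic criterion is for the investigators.

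**Conclusion.** The concern does not call for a change. Objective 4 leaves unwritten how to label an infant who loses IgG between 6 and 18 months, but it states no rule that gives a wrong result. The objective is descriptive and has no test or decision threshold. An analyst meeting such an infant would list it as unresolved and show the number beside the confirmed cases, and with counts this small a reader can recompute the rate either way. The infant with persistent IgG and possible later infection is already not confirmed. The contrast with the Background is one of wording.

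On size: 2.0-2.5 points per infant at 40-50 infants, or 5.0 points at an assumed 20, if the rate is per infant and any infant falls in the window. The documents give no estimate of how many would, and the number may be zero. The conclusion rests on the text shown and on the rate being reported as counts with percentages, as planned.

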#### **Objective 5: Potential mechanisms for vertical transmission**

Currently there is much controversy regarding the possibility of vertical transmission of SARS-CoV-2 infection. There is a need for a systematic approach to characterize the transmission potential of SARS-CoV-2. In order to successfully establish an infection and transmission of the virus in the target tissues, i.e. placenta and developing fetus, SARS-CoV-2 has to be able to dock and invade the placental barrier as well as to overcome the host immunologic response at the site of infection. In order to have a comprehensive investigation of these underlying mechanisms, laboratory tests will be divided into 3 parts to evaluate: 1) placental barrier, 2) immune response and 3) fetal damage of vertical transmission and mechanism in SARS-CoV-2 infection.

Methodology: For the placenta collected from pregnant women affected by COVID-19 (objective 4), dissect it into 10 full-thickness samples (1 x 1 cm) from 10 random sampling sites, away from cord insertion site and far apart from each other. Three of these samples will be stored in 10% buffer-formalin and 2 of them will be stored in EM fixative. For the remaining 5 samples, they will be dissected into 3 parts: chorionic plate, villous and maternal decidua; and store these samples into separate micro-tubes that will be frozen by snap freezing in liquid nitrogen or dry ice and subsequently stored at -80°C.

Placental barrier: we will look into localization, infection, replication and resistance of the viral infection in decidua, amnion, maternal-fetal interface, syncytium and placenta. Tissues and cells from COVID-19 affected pregnancies with live birth (objective 4) and pregnancy loss (objective 2) will be collected and isolated for the study; unaffected pregnancies with live birth and pregnancy loss will also be recruited as control for comparison. Standard scanning EM (SEM) and transmission EM (TEM) will be employed. SEM could provide detailed images of the surfaces of cells, so that the distribution and site of infection of the virion in the maternal, interface and fetal compartments could be located. While TEM provides details of interior structures within the cell, and thus any dysplasia or reconfiguration of cellular organelles due to viral infection could be studied.

Immune response: during viral infection, the virus has to employ host cell surface molecules as specific adhesive receptor. This interaction between the virus and the host cells induces conformational changes on both the viral protein as well as the host plasma membrane, and in turns, promotes viral entry. Viral entry could generally fall into two categories: 1) direct infection of the placenta or 2) indirect infection via transcytosis. Whether SARS-CoV-2 employs direct infection and/or indirect infection through virion transcytosis syncytium will be determined. Results will also correlate with the viral +sense ssRNA load and histologic changes in the corresponding cells. Meanwhile, it has been confirmed that the SARS-CoV-2 invades human cells by utilizing two protein molecules: receptor of angiotensin-converting enzyme 2 (ACE2) which aids in host cell attachment, and a transmembrane serine protease (TPRSS2) which further assists cell entry. The relative abundance, distribution and co-localization of these cell surface proteins in different epithelial, stroma, endothelial, trophoblast, fibroblast and various immune cells will be measured and compared between COVID-19 cases and controls. Efficiency and resistance infection will be measured by viral replication in various human trophoblast primary cells and tissue explants using viral-specific neutralizing antibody titers. Tissue-specific spread, cell-to-cell spread, and bypass of the viral infection will be determined. Nonetheless, not all cells displaying these required receptors are permissive to productive infection. The presence or absence of specific host proteins may also play a critical role during viral infection. Little is known about how these intracellular host factors may influence successful SARS-CoV-2 infection. In order to address this question, we will look into the immunologic reaction of the cells in the decidua, amnion, maternal-fetal interface, syncytium, placental villi core and maternal and cord/fetal blood. Single cell RNA sequencing (scRNAseq) of maternal-fetal interface, maternal blood and cord blood will be conducted in the affected pregnancies with live birth and pregnancy loss. Gene expression of viral infection cascades (e.g. HLA-G, FcRn, TLR, NOD, defensin, etc) and surface molecules (e.g. ICAM, Cadherin, gap junction, etc) in epithelial, stroma, endothelial, trophoblast, fibroblast and various immune cells will be measured and compared with controls. Cell-specific mechanism of immune evasion and defense of SARS-CoV-2 infection for vertical transmission will be determined.

For fetal damage, we will look into the fetal barrier and immune response of the viral infection in the affected fetuses. POC and stillborn babies of affected pregnancies will be collected and isolated for SEM and TEM, ssRNA load qualification, and viral replication to confirm the localization, infection, replication and immunologic reaction as above. If the fetuses have any developmental structural abnormalities identified during antenatal ultrasound examinations, the affected fetal organs, tissues and cells will be specifically collected and studied as above. The results will be correlated with the pathology of the fetuses and compared with the POC and stillborn fetuses of unaffected pregnancies.

Target achievement: We aim to collect 5-10 affected cases with live birth and 5-10 affected cases with pregnancy loss, compared with gestational-age matched controls. We anticipate to characterize and reveal underlying mechanisms for vertical transmission associated with pregnancy loss and fetal complications.

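### Objective 5 compares affected and unaffected tissue on judgement-based readouts, but the protocol specifies no masking or coding of the specimens that are read

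*Protocol*

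**What the plan says.** Objective 5 is set up as a comparison by infection status: "unaffected pregnancies with live birth and pregnancy loss will also be recruited as control for comparison". Its target is 5-10 affected cases with live birth and 5-10 with pregnancy loss, against gestational-age matched controls. The number of controls is not given.

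On the EM methods the text says "Standard scanning EM (SEM) and transmission EM (TEM) will be employed". The readouts that need a reader's judgement are these:

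- Scanning EM, by which "the distribution and site of infection of the virion in the maternal, interface and fetal compartments could be located".
- Transmission EM, by which "any dysplasia or reconfiguration of cellular organelles due to viral infection could be studied".
- ACE2 and TMPRSS2 abundance, distribution and co-localization, which "will be measured and compared between COVID-19 cases and controls". Objective 5 does not name the assay.
- Histology: "Results will also correlate with the viral +sense ssRNA load and histologic changes in the corresponding cells". The reader is not stated.

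On staffing, the Study coordination section says of a clinician scientist and a molecular biologist that "together they will conduct all experiments for objective 5". A further member "will contribute and assist with the interpretation of data for objective 5" and is not described as independent or masked.

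Nothing in the protocol mentions masking, coded specimens or independent reading, and no scoring scheme is given for these readouts.

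**The concern.** Deciding whether a particle is a virion, whether an organelle is abnormal, or whether two proteins co-localize takes judgement. A reader who knows that the tissue came from an infected woman may resolve doubtful images towards a viral effect. The transmission EM sentence already attributes the change to the virus before any image has been read.

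The tissue is selected by infection status and handled by a small team, so that knowledge is readily available unless a step is taken to withhold it. The results will be descriptive and the groups small, so a visible difference between cases and controls is itself the evidence for the mechanism. Masking has to be in place before the first read. An analysis plan written later cannot restore it, so this is not a detail that a protocol can leave to that document.

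**Working it through.** **Step 1: which readouts are exposed.** Exposure needs both a comparison by infection status and a call that depends on a reader.

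| Readout | Compared by status? | Reader judgement? |
|---|---|---|
| Scanning EM, virion site | Yes | Yes |
| Transmission EM, organelle change | Yes | Yes |
| ACE2/TMPRSS2 distribution and co-localization | Yes, stated | Probably; assay not named, but the team's pilot work used immunohistochemistry |
| Histologic changes in Objective 5 | Correlated with viral load and used alongside the comparison | Yes; reader not stated |
| Viral RNA load, single-cell RNA sequencing | Partly | Much less |
| Stillbirth autopsy and placental histopathology (Objective 2) | Described as routine; not assigned to the Objective 5 pair | Much less exposed |
| Gram, periodic acid-Schiff and myeloperoxidase stains (Objective 2) | No; done on positive specimens only | Not a case-control readout |

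The first four rows are the point.

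**Step 2: is there a safeguard?** Sampling sites within the placenta are random. That limits selection of the site but does not mask the reader. The third member who helps with interpretation is not described as masked. No other safeguard was found.

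**Step 3: size.** The plan has no figure to reproduce: the 5-10 per group is a target without a derivation, and no test is stated. The following is an illustration only.

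Input from the protocol: group size n = 5 or 10.

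Assumptions, none from the protocol:
- equal numbers of controls and cases;
- 30% of specimens called abnormal in both groups under masked reading;
- knowledge of status raises the call rate in cases to 50% or 60%;
- a difference of 30 points or more towards cases counts as notable.

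With a abnormal calls in cases and b in controls, independent binomials, the quantity is

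P((a − b)/n ≥ 0.30) = Σ Bin(a; n, p_case) × Bin(b; n, 0.30), summed over a − b ≥ 0.30n.

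| n per group | Net extra calls needed | p_case 0.30 | p_case 0.50 | p_case 0.60 |
|---|---|---|---|---|
| 10 | 3 (3/10 = 30 points) | 0.110 | 0.413 | 0.601 |
| 5 | 2 (2/5 = 40 points) | 0.148 | 0.379 | 0.514 |

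At n = 5, differences move in steps of 20 points, so the 30-point rule is in effect a 40-point rule.

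**Step 4: would it look significant?** Under the same assumptions, a two-sided Fisher exact test at 0.05 gives:

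| n per group | p_case 0.30 | p_case 0.50 | p_case 0.60 |
|---|---|---|---|
| 10 | 1.2% | 5.5% | 12.3% |
| 5 | 1.2% | 4.4% | 8.5% |

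At these group sizes reading bias would therefore show mainly as a descriptive difference and seldom as a significant one.

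**The case against.** The strongest reply is that the protocol is silent and does not prescribe unmasked reading. A reader might infer that the two experimenters will read every image and slide knowing infection status. The document does not say so: conducting the experiments is not the same as reading the images, and no image reader is named. This stands. The point is that masking is not specified, not that reading is stated to be unmasked.

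A reader might also extend the concern to all histology and staining, or to Objective 5 as a whole. That is not supported. The special stains are limited to positive specimens, stillbirth pathology is routine, and RNA load and sequencing depend much less on a reader. EM findings are also to be set beside viral load and replication, which gives some corroboration.

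A third tempting inference is that one or two over-called placentas would be enough to produce the finding. Under the 30-point rule at 10 versus 10 a net three are needed, since two give only 20 points. The rule and the call rates are assumptions in any case.

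Finally, Objective 5 is exploratory and has no decision rule. That rules out any claim about a type I error rate. It does not remove the concern, because with 5-10 per group the descriptive contrast is what readers will rely on. Nothing here touches Objectives 1 to 4.

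**Conclusion.** The concern holds in limited form. Objective 5 contrasts affected and unaffected tissue on EM, protein localization and histologic changes, a small team does the work, and the protocol sets out no coding or masking of the reads. Knowledge of infection status could therefore produce or enlarge a descriptive difference.

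Its size cannot be derived from the documents. The illustrative rise at 10 versus 10, from 11% to 41%-60%, shows sensitivity under assumed call rates and 1:1 controls; it does not measure the bias. The consequence is for the interpretation of mechanism in one exploratory objective. The change is worth making because it is cheap and cannot be made after the images have been read.

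**What to change.** Add to the Objective 5 methodology, covering the placental barrier, immune response and fetal damage parts:

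- EM grids and images, and the protein-localization and histology sections used in the case-control comparison, carry a code.
- The code is held by an existing team member who does not read them.
- All reads are recorded before the code is opened.

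No second reader, extra participant or extra assay is needed. The cost is some re-labelling after preparation, because those who prepare the specimens may know their source, and a code-keeper drawn from the present team. Masking would apply to the reads only, since biosafety labels stay on unfixed tissue. Processing each case in the same run as its matched control is optional good practice and not part of the core change.
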